## 8.8. Sequence and duration of study periods

All patients are followed up until discharge, death, or 28 days post baseline – whichever occurs first.

## 8.9. Schedule of assessments

Data are collected on patients per the CCP-UK Tier Zero schedule and: on each day of RDV dosing, on day 14 after RDV initiation, then on death, discharge or day 28 post hospitalisation, depending which is soonest.

## 9. Listing of outcomes

### 9.1. Primary outcome

14-day mortality

### 9.2. Secondary Outcomes

Secondary outcomes are:

1. Time-to-recovery, where recovery is defined as: discharge from hospital or continued hospitalisation with no on-going health-care needs related to COVID-19
2. 28-day mortality
3. Time-to-death
4. Clinical status at day 15e
5. Length of time receiving supplementary oxygen
6. Time-to-first ventilation
7. Use of non-invasive ventilation at any time during 28 days post baseline
8. Use of mechanical ventilation / ECMO at any time during 28 days post baseline
9. Acute renal injury/acute renal failure at any time during 28 days post baseline
10. Liver dysfunction at any time during 28 days post baseline

Note: length of hospital stay was a key outcome of the SOLIDARITY trial, but is not listed as an outcome here. This is because our cohort includes hospital acquired COVID patients, and some patients with long-term institutionalisation. We are more interested in COVID-related hospital stay, but data on this are not collected beyond 28 days, and so we use the outcome ‘Time-to-recovery’ to double as inference to test whether RDV impacts on short-term length of stay.

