## 17.2.2. Secondary Outcomes

### 17.2.2.1. Time to recovery

Recovery is defined as discharge from hospital or continued hospitalisation with no on-going health-care needs related to COVID-19. For patients that recover, a time-to-event is defined as the number of days from baseline to discharge, or from baseline to cessation of COVID-19 related health-care (whichever occurs first). All other patients are censored at last available follow-up or 28 days (whichever occurs first). All deaths before 28 days (with no prior recovery) will be censored at day 28g. A Cox proportional hazards model will be used to model time-to-recovery, fitting treatment as a covariate, and adjusting for the key confounders: age, sex, and number of comorbidities at baseline. The hazard ratio comparing RDV with controls estimated from the model will be presented together with a 95% CI and a p-value. Kaplan-Meier graphs comparing recovery by treatment group will be presented – for the full matched cohort; and for key age-groups: <50, 50-59, 60-69, 70-79, ≥80 years.

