### 17.2.2.3. Time-to-death

We restrict this analysis to deaths within 28 days of baseline. Any patient alive at the end of the study period will be censored at 28 days. Any patient lost to follow-up prior to 28 days will be censored at their last known follow-up. This outcome will be analysed as a time-to-event using the methodology described in 17.2.2.1 above.

### 17.2.2.4. Clinical status at day 15

Clinical status is defined as an 8-point ordinal score with the following categories: (1) Not hospitalised, and not limited physically; (2) Not hospitalised, but limited physically and/or requiring supplementary oxygen; (3) Hospitalised but medically OK; (4) Hospitalised, not requiring supplementary oxygen, but needs on-going COVID related care; (5) Hospitalised and requiring supplementary oxygen; (6) Hospitalised and requiring non-invasive ventilation; (7) Hospitalised and requiring mechanical ventilation or ECMO; (8) Dead. See Appendix A1.1 below for a definition of how this outcome is derived. Where day 15 CRFs are unavailable, we will look at all available adjacent CRFs to estimate a

---

g We have used the same definition for this outcome as was used in the ACTT-1 trial.

most likely clinical status. In cases where there is ambiguity over likely clinical status, and independent statistical reviewer, blind to all but the clinical status CRF data, will adjudicate likely status. If it is not possible to estimate the outcome, the outcome will be treated as missing.

The outcome will be analysed using a proportional odds model with treatment arm and disease severity as covariates, and adjusting for key confounders: age, sex, and number of comorbidities at baseline. The treatment odds ratio estimated from the model will be presented along with a 95% CI and a p-value.

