## Appendix

Table 1: Clinical status ordinal score at day 15 mapped to ISARIC data fields

Score	Clinical Status	ISARIC v9.3 Data Field(s)
1	Not hospitalised, and no limitations on activities	
OUTCOME CRF (if dated day 15 or less):
 
 
• Discharged alive expected to survive = YES
 
AND
 
• Ability to self-care at discharge = ‘Same as before illness’ OR ‘Better’
 
AND
 
• Oxygen therapy?* = NO
 
 
OR
 
 
• Hospitalisation= YES
 
AND
 
• Medically fit for discharge = YES
 

2	Not hospitalised, limitation on activities and/or requiring home oxygen	
OUTCOME CRF (if dated day 15 or less):
 
 
• Discharged alive expected to survive = YES
 
AND
 
• Ability to self-care at discharge = ‘Worse’
 
OR
 
• Oxygen therapy? = YES
 

3	Hospitalised, not requiring supplemental oxygen – no longer requiring ongoing COVID related medical care	
OUTCOME CRF (dated day 15 or less):
 
 
• Hospitalisation= YES
 
 
AND
 
 
• Ongoing health care needs NOT related to COVID = ‘YES’
 

4	Hospitalised, not requiring supplemental oxygen, requiring on-going COVID related care	
DAILY TREATMENT CRF (day 15):
 
 
• Any supplemental oxygen = NO
 
• Non-invasive respiratory support = NO
 
• Invasive respiratory support = NO
 
• Non-invasive ventilation = NO
 
• High-flow nasal cannula = NO
 
• ECMO = NO
 

5	Hospitalised, requiring supplemental oxygen	
DAILY TREATMENT CRF (day 15):
 
 
• Any supplemental oxygen = YES
 
• Non-invasive respiratory support = NO
 
• Invasive respiratory support = NO
 
• High-flow nasal cannula = NO
 
• ECMO = NO
 

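### Time-to-recovery counts every live discharge as recovery, including one not expected to survive, which Table 1 of the same plan keeps out of its favourable scores

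*SAP*

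**What the plan says.** In the outcome list of SAP section 9.2, "recovery is defined as: discharge from hospital or continued hospitalisation with no on-going health-care needs related to COVID-19". Section 17.2.2.1 repeats the definition: "Recovery is defined as discharge from hospital or continued hospitalisation with no on-going health-care needs related to COVID-19". For a patient who recovers by discharge, "a time-to-event is defined as the number of days from baseline to discharge". The rule for deaths is "All deaths before 28 days (with no prior recovery) will be censored at day 28". Footnote g, called from that sentence, gives the reason: "We have used the same definition for this outcome as was used in the ACTT-1 trial". Section 8.8 sets the end of observation: "All patients are followed up until discharge, death, or 28 days post baseline". The note under section 9.2 adds that time-to-recovery also serves as the inference on short-term length of stay.

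The Appendix (Table 1) builds the day-15 clinical status from the Outcome CRF. Scores 1 and 2, for patients no longer in hospital, list the field "Discharged alive expected to survive" = YES among their conditions.

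**The concern.** The recovery event is meant to mark a good outcome, and section 11 says that hypotheses test for superiority. A patient who leaves hospital alive but is expected to die meets the event definition on the day of discharge. A patient on the same course of illness who dies on the ward is held as not recovered to day 28. The two are scored in opposite ways according to where death occurs.

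The plan's own data source separates these discharges, and the plan uses that separation for one secondary outcome but not for the other. At stake are the recovery hazard ratio, the recovery counts, and the Kaplan-Meier curves for the whole matched cohort and by age group.

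**Working it through.** **How the plan treats a live discharge not expected to survive**

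1. Time-to-recovery: it is an event at the discharge date, because discharge is unqualified.
2. Later death: the rule for deaths applies only where there was no earlier recovery, so the event stands. Follow-up also stops at discharge (section 8.8), so a later death outside hospital is not planned to be captured.
3. Day-15 score: the patient does not meet the survival condition listed under scores 1 and 2, is not in hospital (scores 3 to 7), and is not score 8 unless a death by day 15 is recorded. By elimination the patient has no score.

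The conflict is thus between recovered in one outcome and not classified in the other.

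**Size**

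The SAP gives no event or power figure for time-to-recovery, so there is no stated figure to reproduce. It also gives no rate for these discharges. All recovery and discharge proportions below are assumptions.

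Let F be the proportion counted as recovered by day 28. With deaths kept at risk to day 28, complete follow-up and proportional hazards, 1 − F(RDV) = [1 − F(control)]^HR. Hence HR = ln[1 − F(RDV)] / ln[1 − F(control)]. The definition as written adds the discharges not expected to survive to each F.

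| True recovery, RDV v control | Added discharges, RDV v control | HR without them | HR as written |
|---|---|---|---|
| 70% v 65% | 1% v 2% | ln 0.30 / ln 0.35 = 1.147 | ln 0.29 / ln 0.33 = 1.117 |
| 75% v 70% | 1% v 2% | ln 0.25 / ln 0.30 = 1.151 | ln 0.24 / ln 0.28 = 1.121 |
| 75% v 70% | 2% v 4% | 1.151 | ln 0.23 / ln 0.26 = 1.091 |
| 75% v 70% | 2% v 1% | 1.151 | ln 0.23 / ln 0.29 = 1.187 |
| 70% v 70% | 1% v 2% | 1.000 | ln 0.29 / ln 0.28 = 0.972 |
| 75% v 70% | 1% v 1% | 1.151 | ln 0.24 / ln 0.29 = 1.153 |
| 75% v 70% | 5% v 5% | 1.151 | ln 0.20 / ln 0.25 = 1.161 |
| 70% v 70% | 5% v 5% | 1.000 | 1.000 |

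Each 1% adds 500 × 0.01 = 5 false recovery events per 500 patients, in either group.

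To set the first row against precision, take 500 RDV patients (section 10 expects more than 500) and the maximum 1:4 ratio, so 2,000 controls. Events are 500 × 0.70 = 350 and 2,000 × 0.65 = 1,300. The standard error of the log hazard ratio is about √(1/350 + 1/1,300) = 0.060. The shift is ln 1.1468 − ln 1.1165 = 0.1370 − 0.1102 = 0.027, a little under half a standard error.

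**The case against.** **Comparability is a declared aim.** Section 11 says that outcomes are defined to allow direct comparison with the two earlier trials, and footnote g says that this definition is borrowed from one of them. This stands as a reason to keep the any-discharge version available. It does not justify the difference between the two outcomes: the day-15 score is borrowed from the same trial (footnote e), and there the plan does apply the survival condition.

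**Length of stay.** Any live discharge ends the stay, whatever the prognosis. This also stands: for that second use the definition as written is the better one, and a change to the main definition must not remove it.

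**Table 1 does not score these patients badly.** A reader might infer that the day-15 score counts them as a poor outcome, so that the two endpoints give opposite answers. It does not; it leaves them without a score. For score 2 the conditions are joined by AND and OR without brackets, so on a literal reading a patient discharged on oxygen could score 2 without the survival condition.

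**Direction.** A reader might also infer that the definition favours controls, because patients on a palliative path would less often be given RDV. The SAP does not mention palliative care and gives no rates. Matching on age, vulnerability, comorbidities and HDU/ICU admission (section 8.7) may narrow a difference. The list has no frailty or treatment-limitation variable, so it need not remove one. The direction is open, and equal shares hardly move the ratio.

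**Conclusion.** The concern holds as an inconsistency between two secondary outcomes. Followed as written, the plan records a discharge not expected to survive as a recovery, although a field named in its own Appendix bears on exactly this distinction.

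The size is unknown. Under assumed shares of 1% v 2% the hazard ratio moves by about 0.03, from 1.15 to about 1.12 or, with the groups reversed, to about 1.19. Equal shares of 1% to 5% leave it at 1.15 to 1.16, or at 1.00 when there is no effect. The recovery counts and curves are too high in both groups in every case. These figures rest on assumed recovery proportions, proportional hazards and complete follow-up. The documents do not support a claim that the comparison is biased in a known direction, or by a material amount. The primary outcome, 14-day mortality, does not use this definition.

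**What to change.** In sections 9.2 and 17.2.2.1, state that discharge counts as recovery unless the Outcome CRF records the patient as discharged alive but not expected to survive, and that those discharges are censored at day 28, as for deaths. The day-28 rule is needed. With the condition alone, these patients would fall under the general rule of censoring at last follow-up, which is their discharge date, and that censoring would be informative.

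The recode should need a positive record of such a discharge. Section 18 expects missing data, and a discharge must not become non-recovery merely because the field is blank. The SAP does not show the form's other response options, so the exact coding has to be checked against the CRF.

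Report the number of such discharges by group. Keep the any-discharge definition as a sensitivity analysis, for comparison with the earlier trial and for the length-of-stay inference.

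The cost is one sentence in each section, one recode of a field already in use, and one extra analysis. The main definition then departs by one condition from the borrowed wording. This change does not give these patients a place in Table 1, where they stay unclassified.

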### 7.2. Secondary Objectives

Evaluation of the efficacy of RDV in improving other key outcomes such as speed of recovery, hospital stay, and clinical status over the 28-days post diagnosis in newly diagnosed, hospitalised, non-ventilated severe COVID-19 patients.

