## 12. Confidence Intervals, p-values and Multiplicity

Confidence intervals will be reported for all point estimates at the 95% level. Baseline summaries will be presented to 1 decimal place whilst all other values will be reported to 2 decimal places, or 1 significant figure if it would round to zero at 2 decimal places, and all p-values will be reported to 3 decimal places. There are no planned adjustments for multiplicity.

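### Time-to-recovery is made the test of length of stay, but its hazard ratio mixes mortality with speed of recovery

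*SAP*

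**What the plan says.** Hospital stay is part of a secondary objective (SAP 7.2): "Evaluation of the efficacy of RDV in improving other key outcomes such as speed of recovery, hospital stay, and clinical status". Section 9.2 nevertheless leaves length of stay off the outcome list. Its reasons are that "our cohort includes hospital acquired COVID patients, and some patients with long-term institutionalisation", and that data on COVID-related stay stop at 28 days. Competing death is not among the reasons. In place of a stay outcome, "we use the outcome ‘Time-to-recovery’ to double as inference to test whether RDV impacts on short-term length of stay".

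Section 17.2.2.1 defines the analysis: "A Cox proportional hazards model will be used to model time-to-recovery, fitting treatment as a covariate", adjusted for age, sex and number of comorbidities, giving one hazard ratio with a 95% CI and a p-value. Patients who die without having recovered are not censored at the date of death: "All deaths before 28 days (with no prior recovery) will be censored at day 28". Footnote g gives the reason: "We have used the same definition for this outcome as was used in the ACTT-1 trial".

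28-day mortality and time-to-death are separate secondary outcomes (17.2.2.2 and 17.2.2.3). None of the ten listed outcomes analyses days in care, and none separates recovery from death as competing events.

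**The concern.** One hazard ratio is asked to answer two questions. Holding unrecovered deaths at risk to day 28 makes the model compare how many patients have recovered alive as time passes. That is a sensible composite of survival and recovery. It does not measure how long patients stay. Someone who dies on day 3 counts as 28 days without recovery in this model, although that person spent 3 days in care.

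Lower mortality is the primary objective (7.1), so a mortality difference is exactly what the study hopes to find. Clinicians also choose the treatment (8.7), so residual confounding could produce such a difference. Either way it carries into the recovery hazard ratio and, under 9.2, would be reported as an effect on stay. The reader could then see the mortality effect counted a second time as a shorter stay. A real lengthening of stay among patients who would otherwise have died could also be hidden.

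**Working it through.** **1. The plan's own figure.** The only related numbers are in 17.2.1: 14-day mortality of 3.1% on RDV and 500 RDV patients. 500 × 0.031 = 15.5, rounded up to 16 deaths, and 2 × 16 = 32 under 1:1 matching. Both match the SAP. Control mortality is described only as not lower than on RDV, and no recovery rate is given. Everything below therefore rests on assumed rates, shown as a range.

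**2. Set-up.** Assume living patients recover at the same constant rate in both groups, r = 0.09 per day. Control death rates d are 0.006, 0.012 or 0.025 per day, and RDV has half of each (death hazard ratio 0.5). With s = r + d, over 28 days:

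- mortality = (d/s) × (1 − e^(−28s))
- recovered = (r/s) × (1 − e^(−28s))
- mean days in care to recovery, death or day 28 = (1 − e^(−28s))/s

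Example, highest death rate. Controls: s = 0.115, e^(−3.22) = 0.040, mean days 0.960/0.115 = 8.35, mortality (0.025/0.115) × 0.960 = 20.9%. RDV: s = 0.1025, e^(−2.87) = 0.057, mean days 0.943/0.1025 = 9.20, mortality (0.0125/0.1025) × 0.943 = 11.5%.

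**3. Results (RDV v control).** The planned hazard ratio comes from Cox fits with deaths held at risk to day 28, as 17.2.2.1 specifies.

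| Control death rate | 28-day mortality | Recovered by day 28 | Planned recovery HR | Mean days in care |
|---|---|---|---|---|
| 0.006 | 3.0% v 5.8% | 89.6% v 87.4% | about 1.05 | 9.96 v 9.71 |
| 0.012 | 5.8% v 11.1% | 87.4% v 83.2% | about 1.09 | 9.71 v 9.24 |
| 0.025 | 11.5% v 20.9% | 82.8% v 75.1% | about 1.16 | 9.20 v 8.35 |

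The percentages and days treat time as continuous. Counting part-days as whole days shifts them slightly; the last row becomes about 9.7 v 8.8 days. Depending on this detail the three hazard ratios run 1.04–1.05, 1.08–1.09 and 1.15–1.17.

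In every row the recovery rate among living patients is identical, so the cause-specific hazard ratio is 0.09/0.09 = 1.00. The planned ratio is nevertheless above 1, and it would be read as a shorter stay although mean days in care are longer on RDV. With equal death rates the two groups are identical and the planned ratio is 1.00.

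**4. Distance from the SAP's 3.1%.** 14-day mortality on RDV in these rows is (d/s) × (1 − e^(−14s)):

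- (0.003/0.093) × (1 − e^(−1.302)) = 2.3%
- (0.006/0.096) × (1 − e^(−1.344)) = 4.6%
- (0.0125/0.1025) × (1 − e^(−1.435)) = 9.3%

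The SAP's figure lies between the first two rows, where the distortion is modest.

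**5. Other recovery assumptions.** Taking 3.1% as mortality to day 28 against 6.2% in controls, and median recovery of 5 to 12 days, the planned ratio is 1.04 to 1.10. This holds whether the groups share the recovery rate of living patients or the recovery times of survivors. With an 8-day median and a shared recovery rate, 3.1% v 10% gives 1.12 (10.25 v 9.62 days) and 10% v 20% gives 1.18 (9.62 v 8.70 days).

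**6. Would the cause-specific ratio alone do?** Give survivors identical lognormal recovery times (median 7 days, sigma 0.8) and set mortality at 12% v 18%. The cause-specific ratio is then about 1.09 to 1.11 and rejects at the 5% level in roughly 25% to 45% of simulated trials, depending on assumed death times and matching ratio. A t-test on actual days in care rejects in about 5% to 10%. The cause-specific ratio is a rate among patients still in care, so it is not a sole test of stay either.

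**The case against.** The death rule is deliberate. It follows ACTT-1, and section 11 says outcomes are defined to allow comparison with the trials. Scoring an early death as a short stay would be perverse in a study of benefit. This stands: the definition is sound for time-to-recovery and should stay. A reader might infer that the rule itself is an error, but footnote g and section 11 do not support that. The fault is only the second use in 9.2. The rule also covers only deaths without prior recovery, not every death.

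A mortality effect would be visible elsewhere, since 28-day mortality and time-to-death are reported. That is true and limits the harm, but it does not remove mortality from the recovery hazard ratio that 9.2 assigns to stay.

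A reader might also take the rate at which the planned test rejects in such simulations as a false-positive rate for length of stay. In the third row of the table it is 53% to 75% across 1:1 to 1:4 matching. That reading fails. The SAP never defines the stay null as equal recovery rates among the living, and mean days in care genuinely differ in that scenario, so a t-test on days rejects in about 40% to 60% of trials. The illustration shows that the ratio can have the wrong sign for days in care. It gives no type I error.

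Finally, section 6.1 links EAMS data to cost-effectiveness discussions, but 13.1 says RDV is no longer the subject of an EAMS objective. The point therefore rests on the hospital-stay objective in 7.2, not on commissioning use.

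**Conclusion.** The concern holds for a secondary inference; the primary analysis is not affected. The recovery hazard ratio in 17.2.2.1 combines survival and recovery, so it cannot also serve as the test of length of stay. Its size depends on the mortality difference. It is nil at equal mortality, about 1.05 to 1.09 near the SAP's 3.1% if RDV halves the death rate, and about 1.16 at roughly 20% control mortality. Recovery rates, control mortality and the death hazard ratio are all assumptions. The direction is firmer than the size: in every row of the table the ratio favours RDV while days in care are longer on RDV.

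**What to change.** Keep time-to-recovery and its analysis in 17.2.2.1 as the ACTT-1-comparable outcome. In 9.2, delete the statement that it doubles as inference on length of stay, and describe it as a composite of survival and recovery.

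For the hospital-stay objective in 7.2, add to 17.2.2.1, from the same data and by treatment group:

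- cumulative incidence of recovery and of death to day 28;
- the cause-specific recovery hazard ratio (deaths censored at the date of death), beside the hazard ratio for death, with the adjustment already planned;
- mean COVID-related days in care to recovery, death or day 28, and the difference with a 95% CI. A mean restricted to 28 days would accommodate patients lost to follow-up.

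State that no effect on stay will be claimed from any single hazard ratio, and that these results will be interpreted jointly with mortality. Days in care need this too, because an early death shortens them.

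The cost is SAP wording and a few more secondary estimates from data already derived. No new data are needed.

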## 10. Sample size

This is a prospective observational study of RDV made at the request of the Chief Medical Officer of Her Majesty’s Government. As such there is no formal sample size calculation. We expect a sufficiently large sample size ( $n > 500$  patients treated with RDV satisfying inclusion criteria) to allow meaningful analysis, but there will be no upper boundary placed on the numbers included (data are routinely

---

e This is an outcome defined in the ACTT-1 trial.

collected as part of a wider study). The number of controls cannot be predicted – the ratio of RDV to controls will be at least 1:1, but could be as high as 1:4.

